### **Significance of the study**

The agenda of the United Nations' sustainable development goals (SDG) 2030 is to promote the person with disabilities. Specifically, SDG 3,4,5,6 aimed to achieve good health and wellbeing (end of communicable diseases), quality education (secondary education and conducive learning environment), gender equality (empowerment), and clean water and sanitation (safe and affordable drinking water, sanitation and hygiene especially to girls) of the target population (United Nations ,2016). This project significantly contributes to decreasing the prevalence of malnutrition among school adolescents that will contribute towards partially achievement of SGD,3,4,5 and,6.

This study will help address malnutrition in school-going adolescents. The prevalence of malnutrition is maximum at the adolescent age as it is the most rapidly growing age in both genders. Adolescence is the most important, rapid, and formative phase of human development with unique physical, cognitive, social, and emotional changes taking place. National policies and programs should incorporate the nutritional consequences of this phase of life. The effect of the water, sanitation, and hygiene interventions on nutritional status can better be studied in the adolescent (boys and girls) stage. Another important aspect is that adolescence is a transition from childhood to adulthood, which carries both types of habits along. During preparation for the new demands of adult life, the brain often undergoes complex rewiring processes. With this viewpoint, it can be readily understood that adolescence is a very unique age with additional

dietary requirements to meet the needs of the growth spurt and with the potential to have a significant impact on reproductive health and work, which will in effect affect future generations (Bhutta,2014).

Adolescence is the making or breaking stage of life. Major physical, mental, and psychological growth takes place at this age. Adequate and balanced nutrition is a vital requirement to support this phase. A good nutritional knowledge regarding balance diet for adolescence goes a long way in improving the overall health and producing healthy responsible adults (Bundy,2017).

Adolescents can contribute health of not only themselves but of their families and communities as a whole. The adaptive capabilities of adolescents make them more experimental, exploratory, and risk-taking, which in turn makes this age very appropriate to carry the studies which ultimately improve all aspects of their lives (Dick,2015).

The findings of this study will evaluate the knowledge, attitude, and practices of school adolescents regarding nutrition and WASH. Previous studies have focused on the nutrition intervention of under 5 years of age children or lactating and pregnant women; However, the present study will focus on multicomponent (nutrition, WASH, and deworming) intervention for school-going adolescents. This will be the first kind of its study conducted in a Pakistan setting. The results of this study will serve as a valuable guide for school management and health educators to plan suitable nutrition and health programs. This study will also offer recommendations for school management to adopt similar interventions for nutrition and WASH technique. This will also help them to repeat the same program for other target groups at school or community level. It will also encourage government and other stakeholders for the development of programs and policies related to nutrition and health at schools, districts and province levels. The present study will also add new knowledge to existing practices regarding nutrition and health of adolescents group.

## **Philosophical underpinning**

The study will be guided by the post-positivist paradigm. This paradigm has tended to provide the worldview for most research conducted on human behavior typical of the education context (Kivunja, 2017). Research in this mode requires an ability to see the whole picture, to take a distanced view or an overview. This paradigm allows for observation without experimentation and formulation of hypotheses to be tested.

For clarity purposes, this study will be divided into three phases. Phase I is the formative phase for the development of the intervention module. Phase II is the RCT phase in which the baseline assessment and intervention module will be implemented through the teachers and researcher along with the end-line assessment. Phase III will be research uptake. According to Guba (1990) in post-positivism, reality can never be fully understood but at best only approximated. Data, evidence, and rational considerations shape knowledge. The researcher will collect information on instruments based on measures completed by the participants or by observations recorded by the researcher. Being objective is an essential aspect of competent inquiry; the researcher will examine methods and conclusions for bias like the standard of reliability and validity.

## **Framework**

For this study, a socio-ecological approach will be adopted because to change the behaviors of individuals permanently, changes in the environment has to take place (Wang, 2016). Based on the work of Urie Brofenbrenner, Lori Heise & McLeory in 1998 offered a theory-based framework for understanding the multi-layered and interactive effects of personal and environmental factors that determine behaviors such as smoking, physical activity, nutrition, sexual activity, and intermediate health promotion. This framework consists of five levels that are used in different setting at different levels. These levels include **intrapersonal**,

**Interpersonal, Institution, Community, and Policy. (Fig 1).** Regardless of topic, setting, and time period, most of the studies describe intrapersonal or interpersonal level activities with easily measurable objectives, while community and policy level activities are much less due to training of the health educators or resources to plan and implement institution, community, or policy level programs. However, few studies showed school-based intervention used three or more levels. (Level, 2002 & Golden, 2012). Furthermore, this model not only influence the health behavior of the target population, but also for the execution of health/ nutrition education, and WASH practices (Golden, 2012.) Therefore, this study will use the school health environment, school nutrition and WASH program, and family and community involvement based on the socio-ecological model to design the intervention at all levels.

[figure not shown]
**Intrapersonal:** At intrapersonal level knowledge, attitude, and practice regarding nutrition and WASH will be assessed. Skill-based education will be provided to the adolescents regarding healthy diet and WASH. Furthermore, monitoring of micronutrient levels and, deworming will be carried out.

**Interpersonal:** At the interpersonal level, involvement of mothers/immediate caretaker, teachers and school management and nutritionist will be ensured. Perception of the adolescent's mother/immediate caretaker and teachers will be assessed regarding nutrition and WASH practices. Peer lead, "adolescent to adolescent" approach will be used to develop a friendly environment to train the adolescents.

**Institution level:** Modification of the school environment, module development for focus areas and change in the school curriculum will be worked out.

**Community level:** Vendors outside the school will be assessed for food quality and type. Parents and community stakeholders will be involved

**Policy level:** Findings of the study will be shared with the national nutrition program managers and with district education and health officer and advocate the issue at all levels to influence the policy makers. At policy, level there can be nexus of the health ministry and the educational system. However, there will be limitations to influence the policy makers, for example, political instability (high turnover of leadership), lack of political will, dissension among the leadership between the health and the other division of government, resistance from the professional or regulatory bodies, system requirement (human resource), contradictory policies, fair allocation of budget, and lack of social accountability by policymakers.

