Healthy diet education	
 
• Health education session
 
• Role play
 
• Quiz and games
 
• Flip charts
 
• Log books for food intake
 
• Peer education through a group presentation
 
• Incentive for healthy lunch
 
	Early school adolescents (6,7,8 grade)	School teachers	
 
• Module on Healthy diet
 
• 30-45 min session on nutrition on a weekly basis for 12 weeks
 
• Poster and Charts
 
• Flip charts with key messages
 

	
 
• Take-home cooking recipes based on local context and food available
 
	Mother/immediate care taker	
 
• Through adolescent (6,7,8, grade)
 
	
 
• Diary/log books
 

Water, Sanitation, and Hygiene (WASH)	
 
• Showing video on steps of hand washing
 
• Demonstration of hand washing technique
 
• Take home handout
 
	Early school adolescents (6,7,8 grade)	
 
• School teachers
 
	
 
• Module on WASH
 
• 30-45 min session on WASH on weekly basis for 4 weeks
 
• Charts and posters
 

The proposed intervention will be finalized after formative assessment (FGDs with teachers and mothers and KI with school management).

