##### ***Baseline assessment***

Knowledge, attitude, and practices regarding nutrition and WASH will be assessed among school adolescents through a KAP survey along with anthropometric

measurement, physical assessment, and micronutrient assessment (CBC, Zinc, Calcium,).

The observation on the eating and WASH practices of grade 6-8 adolescents will be done by the researcher during break time (lunch time) and school off timings.

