### **Data collection tool/instrument**

Data will be collected through adopted and adapted self-administered, structured questionnaires from 6,7, and 8-grade school-going adolescents at baseline and the end line. The questionnaire will be categorized into four main groups to assess the respondent's demographic data and their knowledge, attitude, and practices (KAP) about nutrition and WASH. Group A (demographic characteristic), group B contains physical assessment, group C included 24 Questions on KAP on nutrition that are adopted from the KAP manual developed by the Food and Agriculture Organization of the United Nations (2014) and group D are based on the 16 WASH items adopted from GSHS version 2013. The questionnaire will be translated into the Urdu language. Observation of the eating practices, school canteen, WASH, and school environment will be assessed through a checklist at baseline and end line.

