### **Activities of baseline assessment**

Activities	Purpose	Frequency
KAP survey	To know the KAP regarding nutrition and WASH	Baseline and end line
Anthropometric measurements	To identify the number of thin, underweight, Overweight, and Obese adolescents in 6-8 grade	Baseline and end line
Physical assessment	To identify the health status of adolescents	Baseline and end line

Monitoring CBC, Zinc, Calcium, and Vitamin D level	To identify the deficiency of micronutrients at baseline and improvement at the end line	Baseline & end line
Observations	To assess the practices related to major determinants of malnutrition i.e. nutrition, water, sanitation, and hygiene.	Baseline & end line

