### Data analysis plan

Quantitative variables will be described by means and standard deviations whereas median with interquartile range will be mentioned for qualitative variables. Frequencies and percentages will be calculated for the knowledge, attitude, and practices of adolescents regarding nutrition and WASH. The comparison between intervention and control at baseline and end line will be performed by using paired t-test and Chi-square. For the variables that are not normally distributed, a nonparametric test McNamara will be used. Binary logistic regression and multiple linear regression will be used to assess the effect of intervention. All the statistical analyses will be conducted using SPSS version 23. A p-value less than 0.05 will be considered statistically significant.

Descriptive	Inferential

 
• Mean, SD Normally distributed
 
• Median, interquartile range Skewed distribution
 
• Percentages and frequencies of knowledge, attitude, and practices
 
	
 
• Chi-Square-McNamara knowledge, attitude, and practices
 
• T- test paired Continuous variables
 
• Binary logistic regression and multiple linear regression
 
• Proportion changes - chi-square Observational checklist
 

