**Intervention**

The intervention will be planned based on a socio-ecological model and health-promoting school framework. School health environment, health education, health services, and nutrition programs will be focused in the intervention stage of the study.

Based on the formative assessment, the module will be developed in consultation with Nutritionist, the research team, and recent literature. For the validity of the module, expert opinions will be taken from the nutritionist, school education, and WASH experts. Two to three workshops will be arranged for school teachers to train them as master trainers who are teaching 6 to 8-grade school-going adolescents. Sixteen sessions (one session per week) will be arranged on nutrition education and water, sanitation, and hygiene for adolescents. Micronutrient tablets will be administered to adolescents for three months daily through school teachers. Moreover, 6-8 grade adolescents will be dewormed before and after the intervention. In addition, Cooking recipes in the local language will be shared with the adolescent's mother/immediate caretakers through adolescents. Different strategies will be used in the study sessions like demonstrating and showing videos on hand washing, role play, quiz etc.

During the intervention phase, there are no such risks involved to the study participants except their valuable time. Due to deworming and micronutrient supplementation, there may be temporary dizziness, nausea, headache, constipation, and dark color stool along with discomfort from prick for blood drawing from adolescents. To reduce the temporary side effects of deworming administration, the researcher will advise them to keep adequately hydrated themselves and take the micronutrient supplementation tablet. Reassurance regarding drawing

the blood samples will be done. The existing referral system will be identified and utilized if needed

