### **Post-intervention phase:**

A KAP questionnaire administered before intervention will be used to assess the changes in knowledge, attitude, and practices of school adolescents in the post-intervention phase. Anthropometric measurement, micronutrient assessment, and physical assessment will also be done to assess the effectiveness of the intervention. Moreover, the checklist will also use to evaluate the changes in the School environment and WASH practices.

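### School environment is both something the intervention changes and an end-line checklist domain tested by chi-square, with nothing marking it as delivery data

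*Protocol*

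**What the plan says.** **As part of the intervention.** The Framework section, at institution level, commits the study to this: "Modification of the school environment, module development for focus areas and change in the school curriculum will be worked out". The Intervention section (Phase II) repeats the idea: "School health environment, health education, health services, and nutrition programs will be focused in the intervention stage of the study".

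**As something measured.** The Data collection tool/instrument section states: "Observation of the eating practices, school canteen, WASH, and school environment will be assessed through a checklist at baseline and end line". The Post-intervention phase section then says that "the checklist will also use to evaluate the changes in the School environment and WASH practices".

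**As something tested.** In the Phase II Data analysis plan, the table's inferential column assigns the observational checklist the entry "Proportion changes - chi-square". The text of that section sets 0.05 as the threshold for significance in all analyses.

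**Control arm.** The Study design section allows a drinking-water installation at control schools if money is available, and gives no timing for it.

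**The concern.** A checklist domain that the team itself sets out to alter cannot show whether the intervention works. If the team modifies the environment of the intervention schools, the end-line checklist will record that modification. This would be so even if no pupil learned anything or ate differently. A significant chi-square on such an item would show that the programme was delivered, yet under the plan as written it would stand among the trial's inferential results.

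The plan never separates the two kinds of checklist content. Pupil practices (what adolescents eat, whether they wash their hands) respond to the intervention and are reasonable behavioural outcomes. School environment and canteen features can be installed or rearranged directly by the team. Both kinds sit on one checklist under one test. A report could then claim an improved school environment as a finding when it was an input.

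**Working it through.** The point rests on comparing sections; the plan gives no figure to reproduce.

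**Step 1: is the environment delivered?** Yes, in two places: Framework (institution level) and Intervention. The content is left open. The exposure list, the Study design description of the intervention arm and the activity table name no specific change to canteen or facilities.

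**Step 2: is it measured at end line?** Yes. School canteen and school environment are named checklist domains, at baseline and end line.

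**Step 3: is it used to evaluate?** Yes. The Post-intervention phase section uses the checklist to evaluate change in the school environment.

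**Step 4: is it tested?** Yes. The checklist stands in the inferential column with a chi-square, not among the descriptive entries.

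**Step 5: is it labelled as delivery data anywhere?** No. The only stated purpose of the observations, in Activities of baseline assessment, is "To assess the practices related to major determinants of malnutrition i.e. nutrition, water, sanitation, and hygiene". That describes behaviour and does not fit an environment item.

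**Step 6: what would the test do with one such item?** This is an illustration, not an estimate. Assume that an item is recorded once per school, that the team changes it in both intervention schools, and that neither control school changes. The Study Setting section gives two schools per arm, so the end-line table is 2 of 2 against 0 of 2.

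- Pearson chi-square without correction: n(ad − bc)² / (product of the four margins) = 4 × (2×2 − 0×0)² / (2×2×2×2) = 64/16 = 4.0 on 1 degree of freedom, p = 0.046. This is nominally below 0.05, with no pupil behaviour involved.
- Randomisation reasoning: one boys' and one girls' school go to each arm, so there are 2 × 2 = 4 possible assignments. Two of these give a contrast this large in one direction or the other, so the two-sided p is 2/4 = 0.50.

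On these assumptions the planned test could label a delivered item significant, although four schools cannot support that inference. The plan does not state the checklist's unit of recording, and the water provision for control schools means that the no-change assumption for controls may fail. The example therefore shows the mechanism only.

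**The case against.** The strongest reply is that little depends on this domain. The lists under Outcome of the study and Measurement of Exposure and Outcome contain BMI, micronutrients, physical examination and KAP, and omit the checklist. In the Post-intervention phase section, the sentence about effectiveness names anthropometric, micronutrient and physical assessment; the checklist follows in a separate sentence without that word. The hypothesis and objectives concern malnutrition, nutritional status and micronutrient levels. The environmental changes are undeveloped, and every school must already have working WASH facilities to enter. All of this stands, and it limits the point to a reporting matter. It does not remove it, because the Protocol itself gives the checklist an evaluative role and an inferential test.

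A reader might also infer that the lunch reward raises the same problem, since "Incentive for healthy lunch" is an intervention strategy and eating at break time is observed. The documents do not support this. Giving the incentive is not listed as a checklist domain. What is observed is pupil conduct: "The observation on the eating and WASH practices of grade 6-8 adolescents will be done by the researcher during break time (lunch time". A behavioural response to a randomised package is an effect of that package. The activity table also places the incentive in the four-month intervention phase and end-line observation in a separate two-month post-intervention phase.

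**Conclusion.** The point holds for the school environment and canteen domain. The Protocol names the school environment as something to be modified, observes it and the canteen at end line, and tests the checklist at the 0.05 level without marking these items as delivery data. Following the plan would present the team's own modifications as a trial result.

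The size cannot be stated, because neither the modifications nor the individual checklist items are given. The conclusion assumes only that the team makes some change in this domain, as the Framework and Intervention sections say it will.

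Two broader readings go too far. One is that the trial as a whole counts delivery as effect; the conclusion on malnutrition rests on other measures. The other is that environment items can change in the intervention arm only; the possible water installation means that control schools may change too.

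**What to change.** In the Phase II Data analysis plan and the Post-intervention phase section:

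- Report school-environment and canteen items as implementation measures, described for each of the four schools at baseline and end line, with no significance test.
- Cover both arms, and record there any water facility given to a control school.
- Keep observed pupil eating and WASH practices separate. They may remain behavioural outcomes, read as effects of the whole package.

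Since the intervention is to be finalised after the formative assessment, the rule is best written before the modifications are chosen. This is a change of wording and reporting that needs no new data. The downside is that fewer checklist items can be claimed as effects.

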**Purpose of the study**

To determine a school-based nutrition education and water, sanitation, and hygiene intervention to improve nutritional status among early adolescents.

**Hypothesis**

$H_0$  = There will be no effect of nutrition education and WASH intervention on the prevalence of malnutrition among 6-8 grade school going adolescents.

$H_1$  = There will be a reduction in the prevalence of malnutrition among 6-8 grade school going adolescents through nutrition education and WASH practices.

**Exposure of the study**

1. Nutritional and WASH education module for four months
2. Micronutrient supplementation for three months

**Outcome of the study**

The main outcome is the reduction of malnutrition among school going early adolescents (6 to 8 grade) in a school setting that will be assessed through;

1. Body Mass Index
2. Micronutrients
3. Physical examination
4. Knowledge, attitude, and practices regarding nutrition and WASH

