**b. Dependent variables/Outcome of study**

1. Body Mass Index: All school going 6- 8 grade adolescents will undergo anthropometric measurements such as height, and weight (BMI). The measurement will be taken at baseline and end line by using WHO standard growth chart.
2. Micronutrients: Blood sample will be collected twice (baseline and end line) from a subset of 108 adolescents (54 intervention group,54 control group). The blood samples will help to assess the impact of intervention on micronutrient deficiencies (Iron, Zinc, Calcium, CBC, Vitamin D)
3. Physical examination: Physical examination like hair, skin, nail, eye (bitot spot), mouth (dental caries), and goiter will be assessed for micronutrient deficiencies at baseline and end line.
4. Knowledge, attitude, and practices regarding nutrition and WASH: a structured questionnaire will be used to collect data on nutrition and WASH-related indicators. The survey will be administered at baseline and end line. The indicator assessed will be adolescent health status and knowledge, attitude, and practices regarding nutrition and WASH practices.

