### **Secondary objective**

To measure the impact of school-based nutrition education and water, sanitation, and hygiene intervention on micronutrient levels among early adolescents.

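### The main outcome is spread over four unranked measures, in conflict with the protocol's own hypothesis, sample size, secondary objective and expected outcomes

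*Protocol*

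**What the plan says.** Protocol, Outcome of the study: "The main outcome is the reduction of malnutrition among school going early adolescents", to be assessed through a numbered list of four measures. These are body mass index, micronutrients, physical examination, and "Knowledge, attitude, and practices regarding nutrition and WASH". No lead measure, composite rule or order is given. The section on dependent variables repeats the four, with the blood measures given as "Iron, Zinc, Calcium, CBC, Vitamin D".

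Other sections of the protocol bear on the same question:

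- **Secondary objective:** "To measure the impact of school-based nutrition education and water, sanitation, and hygiene intervention on micronutrient levels among early adolescents".
- **Primary objective:** improvement of nutritional status, with no variable named.
- **Hypothesis:** "There will be a reduction in the prevalence of malnutrition among 6-8 grade school going adolescents", credited to nutrition education and WASH practices.
- **Sample size (RCT phase):** 180 pupils per arm, 42% malnutrition assumed in the control arm, a 6% reduction, two-sided 5% level.
- **Expected outcome:** nutritional status is described through BMI moving up into the normal range, and better KAP is a separate item.
- **Activities of baseline assessment:** anthropometry serves to count thin, underweight, overweight and obese pupils.
- **Data analysis plan (RCT phase):** "A p-value less than 0.05 will be considered statistically significant", with no distinction between main and other outcomes.

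**The concern.** A reader cannot tell from the outcome section which result answers the trial's question. Micronutrients are both a measure of the main outcome and the subject of the secondary objective. KAP is listed as a measure of malnutrition, although it is not one and the protocol elsewhere keeps it apart.

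This matters because some of the listed measures can change while prevalence does not:

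- **KAP** comes from a self-administered questionnaire on topics that intervention pupils are taught over sixteen weekly sessions.
- **Blood levels** are measured in 108 of the 360 pupils. The intervention includes a daily micronutrient tablet for three months, so levels could rise from the tablets alone, while the hypothesis credits education and WASH.

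Under the present wording, either change could be presented as a result on the main outcome. Once the data are seen, a choice among the four would not be credible.

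**Working it through.** **Step 1. Set the sections side by side.**

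| Section | What it treats as the result of interest |
|---|---|
| Outcome of the study | BMI, micronutrients, physical examination and KAP, unranked, under one main outcome |
| Primary objective | Nutritional status, no variable named |
| Secondary objective | Micronutrient levels |
| Hypothesis | Prevalence of malnutrition |
| Sample size | Prevalence of malnutrition (42% in controls) |
| Expected outcome | Nutritional status through BMI; KAP listed separately |

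The hypothesis and the sample size agree with each other. Expected outcome and the anthropometry row of the activities table point to BMI as the way status is judged. The outcome section is the outlier: its micronutrient entry conflicts with the secondary objective, and its KAP entry conflicts with Expected outcome.

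**Step 2. Size of the problem if all four are taken as main outcomes.** The protocol gives no overall error rate for the main outcome, so there is no stated figure to reproduce beyond the 5% threshold.

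Inputs: k = 4 measures (Outcome of the study) and a threshold of 0.05 (Data analysis plan). Assumptions: one test per measure, each test truly holding its 5% level, and no true effect on any measure. The protocol gives no correlation between measures, so a range is shown.

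- Independent tests: 1 − (1 − 0.05)^4 = 1 − 0.8145 = 0.185, or 18.5%.
- Correlated tests: four standard normal statistics with a common correlation, 400,000 simulated draws, counting those where any absolute value exceeds 1.96.

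| Assumed correlation | Chance of at least one false positive |
|---|---|
| 0 | 18.5% |
| 0.3 | 17.4% |
| 0.5 | 15.6% |
| 0.8 | 11.4% |

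**Step 3. What the alternatives give.**

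- One named primary measure tested at 0.05: 5%.
- All four kept as main outcomes, each at 0.05/4 = 0.0125: at most 5%, and 1 − 0.9875^4 = 4.9% if independent.

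The sample-size statement is used here only to identify the endpoint that the trial was sized on. Whether 180 per arm delivers the stated power is a separate matter and does not affect this point.

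**The case against.** The best defence is that the intended primary can be inferred. The primary objective, hypothesis, sample size, baseline activities table and Expected outcome together point to BMI-based malnutrition. On that view the list in the outcome section is a loose inventory of measures and not a declaration of four co-primary endpoints. This largely stands, and it shows which repair fits the trial. It does not remove the conflict: the section that defines the outcome still says something different, and it carries the label of main outcome.

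The second defence is scope. Multiplicity adjustment, testing order and KAP scoring commonly sit in a statistical analysis plan, which is not at hand. A general 0.05 threshold is ordinary and is not an error in itself. This stands too. The choice of main outcome and the double role of micronutrients, however, are fixed in the protocol and have to be put right there.

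A reader might infer three stronger things that the document does not support:

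- *That success may be claimed on any one of the four.* The protocol states no success rule. It permits that reading without declaring it.
- *That the error rate is far higher because KAP items are tested one by one.* The questionnaire has 40 items ("group C included 24 Questions on KAP on nutrition", plus 16 on WASH). The analysis table names a test for KAP but never says that items are tested singly. Independence among items answered by the same pupils would also be implausible.
- *That each blood marker counts as a separate main test.* CBC is a panel, and iron is missing as a separate item from several of the protocol's own lists of blood tests. The number of laboratory tests is therefore not settled by the text.

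**Conclusion.** The concern holds as an inconsistency in the protocol's definition of its main outcome. Four unranked measures sit under that label, while the hypothesis and sample size use prevalence only, micronutrients are the secondary objective, and KAP is elsewhere kept apart from nutritional status.

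The consequence is room for selective emphasis. If the four were all treated as main outcomes at 0.05, the chance of at least one false positive would be about 11% to 19% instead of 5%. That range rests on one test per measure, each at a true 5% level, and an assumed common correlation from 0.8 down to 0. A correlation above 0.8 would bring the figure closer to 5%. The case for naming one primary rests on the conflict between sections and does not depend on where in the range the true value lies.

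**What to change.** In Outcome of the study, name one primary outcome: the prevalence of malnutrition at end line, defined by BMI-for-age on the WHO growth chart that the protocol already uses.

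State which BMI categories count as malnutrition. Naming prevalence alone would not be enough, because the Introduction's classification of malnutrition also covers micronutrient deficiency and overweight. Within BMI, the baseline activities table lists both under- and overweight categories, while Expected outcome speaks only of BMI rising to normal. The chosen definition should be the one to which the assumed 42% refers, and the sample-size section should say so.

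List micronutrients as secondary, matching the secondary objective, and KAP and physical signs as secondary or exploratory. Add to the Data analysis plan that the trial's conclusion rests on the primary outcome.

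The cost is protocol wording only. The small downside is that KAP or laboratory results alone can no longer be called the main result.
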